**3. Abstract:**

More Americans suffer from pain than are affected by heart disease, cancer and lung disease. Opioids represent the cornerstone of pain management, yet analgesic responses to opioids are widely variable. Opioid prescriptions have tripled since 1999, paralleled by increases in opioid-related hospitalizations and deaths, contributing to the opioid epidemic. Approximately 35% of all opioid prescriptions originate from surgeons. Hydrocodone, tramadol, and codeine are among the most commonly prescribed opioids, and the cytochrome P450 enzyme, CYP2D6, is central to generation of highly potent metabolites for these opioids. CYP2D6 genotype leads to absent, reduced, normal, or increased function, conferring poor (PM), intermediate (IM), normal (NM) and ultrarapid (UM) metabolism phenotypes, respectively. Data suggest avoiding hydrocodone, tramadol, codeine, and oxycodone in PMs, IMs and UMs because of increased risk for poor response (IM and PM) or toxicity (UM). Leveraging our experience from a recent study, we will test the ***hypotheses that CYP2D6 genotype-guided management of post-surgical pain 1) is feasible, with reduced use of codeine, tramadol, hydrocodone, and oxycodone in PMs/IMs/UMs and 2) will improve post-operative pain control in PMs/IMs***

**and reduce DEA Schedule II (C-II) opioids in NMs.** Patients scheduled to undergo arthroplasty surgery will be recruited from the UF Health Gainesville and the Villages Orthopedic clinics. Patients will be randomized 2:1 to a genotype-guided versus usual care approach. For patients with CYP2D6 PM, IM or UM phenotype based on genotype or drug interactions, a recommendation to avoid hydrocodone, tramadol, codeine, and oxycodone will be made. In others, tramadol will be recommended, given evidence of its lower potential addiction risk than C-II opioids. Patient Reported Outcomes Measurement Information System (PROMIS) measures will be administered at baseline (within 30 days of surgery) and 2 weeks  $\pm$  4 days post-surgery for patients in each arm. Pain scores and assessments of physical functioning, emotional functioning, and mobility from the PROMIS measures and utilization of pain medications during the 2 week period following surgery will be compared between groups.

#### **4. Background:**

In the past 10 years, there have been significant advances in defining genetic determinants of drug response. These advances have led to the expectation by many that eventually an individual's personal genetic information will become part of his or her medical record to be used to guide treatment decisions. The UF Health Personalized Medicine Program (PMP) was created at UF to meet this expectation. The initial efforts of the PMP involved implementation of cytochrome P450 (CYP) 2C19 genotyping to guide antiplatelet therapy following percutaneous coronary intervention. We have since implemented *TPMT* testing to guide thiopurine dosing, *CYP2D6/CYP2C19* testing to guide selection of serotonin reuptake inhibitors, *CYP2C19* genotyping to guide proton pump inhibitor dosing, and *CYP2D6* testing to guide opioid prescribing in primary care.

The gene for *CYP2D6* is highly polymorphic, with over 100 alleles defined. Functional variation within *CYP2D6* includes SNPs, insertions, deletions, and instances where the gene is deleted or duplicated. Approximately 5-10% of individuals are poor metabolizers (PMs), with no active *CYP2D6* enzyme secondary to frameshift mutations (\*3, \*6), splicing defects (\*4), or complete gene deletion (\*5). Another 2-11% are intermediate metabolizers (IMs), with significantly impaired enzyme activity secondary to having both a nonfunctional and reduced function *CYP2D6* allele. At the opposite extreme, approximately 1-2% of individuals are ultra-rapid metabolizers (UMs) with *CYP2D6* gene duplication/multiplication. Numerous commonly used drugs inhibit the *CYP2D6* protein and can convert one's phenotype to PM or IM, which is called phenoconversion.

Codeine and tramadol are dependent on bioactivation by the *CYP2D6* enzyme to morphine and O-desmethyltramadol, respectively, which have 200-fold greater affinity for the  $\mu$ -opioid receptor than their parent compounds. IMs and PMs have impaired generation of the active metabolites of codeine and tramadol, and may derive little to no pain relief from these drugs. Interestingly, the occurrence of central side effects may not differ between PMs, IMs, and normal metabolizers (NMs) so that while PMs and IMs may get little to no pain relief from opioid analgesics, they may still experience troublesome adverse effects. Conversely, UMs are at increased risk for toxic concentrations of active opioid metabolites, with reports of life-threatening toxicity and death with codeine or tramadol. Hydrocodone and oxycodone undergo similar metabolism via *CYP2D6* to hydromorphone and oxymorphone, respectively, which have 10- to 40-fold higher receptor affinity than the parent compound. In the case of hydrocodone, tramadol, codeine, and oxycodone, our preliminary data below, and data from others, suggest these drugs should be avoided in PMs and IMs for lack of efficacy and in UM because of toxicity risk.

The rapid increase in opioid prescribing in the last 20 years is paralleled by increases in opioid-related hospitalizations and deaths and significant societal costs. Opioid misuse contributed to over 60% of all drug-related deaths in the U.S. in 2015, and in the majority of cases, the opioid was obtained legally through prescription. **The majority of individuals who misuse opioids report that their motivation for doing so is to relieve physical pain, highlighting the need for better measures to improve pain control and opioid prescribing.** A major gateway to chronic opioid use arises from post-operative opioid prescribing, with evidence of persistent opioid use in approximately 6% of opioid naïve individuals receiving a new opioid prescription after an outpatient surgical procedure. With this risk, there is a critical need to identify ways to control pain while minimizing use of highly addictive opioids, like hydrocodone and oxycodone.

Guidelines support *CYP2D6* genotype-guided use of opioid analgesics, but this is rarely done in clinical practice. We propose a pilot trial in patients with acute post-surgical pain in which we will make recommendations based on *CYP2D6* genotype and *CYP2D6* enzyme inhibitor drug interactions that can convert individuals to the PM or IM phenotype. In PMs, IMs and UMs, we will recommend avoidance of hydrocodone, tramadol, codeine, and oxycodone and for NM, tramadol will be recommended as the preferred opioid, given its opioid and non-opioid mechanisms and purported lower risk for misuse. One study suggested the potential for abuse and dependence with tramadol in patients with chronic non-cancer pain was significantly less than for hydrocodone, and not different from that of non-opioid pain relievers. The preference toward tramadol is consistent with the Enhanced Recovery After Surgery Pathway, which proposes a strategy to limit peri- and post-operative opioid use and combat the opioid epidemic through primary use of non-opioid agents and techniques and tramadol as the preferred opioid for breakthrough pain because of its evidence for lower addition. We will examine the effect of having *CYP2D6* genotype information on pain management and pain control. Findings will inform a larger trial of the efficacy of a genotype-guided approach to pain management. The ultimate goal of this line of research is to reduce the significant societal burden associated with pain. While not directly assessing the opioid epidemic, reduced use of more potent and addictive opioids for the management of post-surgical pain may lead to less persistent opioid use.

[figure not shown]
#### **4a. Preliminary Studies:**

***CYP2D6* genotype-guided pain therapy.** We conducted a pragmatic clinical trial to test the potential clinical benefit of *CYP2D6* genotype to guide tramadol, codeine, oxycodone and hydrocodone in patients with chronic pain (NCT02335307). We enrolled 480 patients with  $\geq 3$  months pain from 9 different primary care clinics at UF Health or the OneFlorida Network. Patients were randomized 2:1 to a genotype-guided intervention or control group (usual care, with genotype reported at study end). NIH-developed and validated Patient Reported Outcomes (PRO) Measures Information System (PROMIS) pain measures were collected from all patients at baseline and 3 months. For the genotype group, genotype data were available approximately 7 days after the baseline clinic visit. Patients were defined as phenotypically *CYP2D6* UMs, NMs, IMs or PMs based on their *CYP2D6* genotype and use of strong or moderate *CYP2D6* inhibitors (according the FDA guidelines). A clinical pharmacist-written consult note was provided on all patients with an actionable (PM, IM, or UM) phenotype. Strong recommendations were made in IMs and PMs against tramadol and codeine, where the impact of *CYP2D6* is clear. Recommendations against oxycodone and hydrocodone were more moderate. Acceptance of the recommended changes was at the physician's discretion. At baseline, median pain intensity based on PROMIS measures was 6.7/10, and 438/480 (91%) were taking an opioid, which included 164 on tramadol, 96 on hydrocodone, 11 on codeine, 125

Protocol #: 201800445

Version Date: 10/02/2019

on oxycodone and 42 on other opioids. Based on genotype, 1% were UM, 11% were IMs or PMs, and when considering phenoconversion by strong or moderate CYP2D6 inhibitors, 29% were IMs or PMs. Patients treated with tramadol, hydrocodone or codeine at baseline had improvements in the genotype-guided arm in pain intensity. In the group for whom the benefit was expected (IMs and PMs), analyses revealed significantly greater improvements for genotype-guided versus usual care for numerous pain intensity subscales (Figure 1). A clinically meaningful 30% reduction in pain score was observed in 24% of genotype guided versus 0% of usual care patients ( $p=0.04$ ). There was also a significant reduction in pain intensity when also considering hydrocodone use at baseline ( $p=0.02$ ).

## 5. Specific Aims:

The specific aims of our pilot study are to: 1) test the feasibility of a genotype-guided opioid prescribing approach for patients undergoing an outpatient surgical procedure, a group at high risk for persistent opioid use; and 2) evaluate the effect of genotype-guided post-surgical pain management on pain control and opioid prescribing. This will be a randomized, open-labeled pilot pragmatic clinical trial. A total of 320 patients will be recruited from the UF Health Gainesville and the Villages Orthopedic Clinics during their Initial Evaluation for total joint (hip or knee) replacement once the decision for surgery is made. For patients randomized to the genotype-guided arm, a saliva or buccal cell sample will be collected unless venipuncture is done for other reasons and then a blood sample will be collected for genotyping. Genotyping will be performed in the UF Health Pathology Laboratory and results placed in the electronic health record (EHR). For patients in the usual care arm, a genetic sample will be collected for clinical genotyping at the end of the study. At baseline (within 30 days of surgery) and 2 weeks  $\pm$  4 days after surgery, all patients will be asked to complete the PROMIS measures for assessment of pain intensity, physical functioning, emotional functioning, mobility, and a measure of medication misuse. We will also assess utilization of pain medications during the 2 weeks  $\pm$  4 days following surgery. We hypothesize that CYP2D6-guided post-operative pain management is feasible, with reduced use of codeine, tramadol, hydrocodone, and oxycodone in patients with the PM, IM, or UM phenotype, and will improve pain control in PMs and IMs and reduce use of more addictive opioids (i.e. DEA schedule II opioids) in patients with the NM phenotype.

## 6. Research Plan:

The study will be a randomized, open label pragmatic clinical trial in 320 patients undergoing total joint arthroplasty, who will be randomized to genotype-guided opioid therapy or usual care.

We will collect data on the implementation success metrics, PROs via PROMIS measures, and for opioid utilization measures, we will collect proportion of patients prescribed specific opioids and self-reported opioid use, since patients may not take any or all of the opioid prescribed.

Inclusion Criteria. A total of 320 patients scheduled to undergo total joint arthroplasty at UF Health will be recruited from the UF Health Gainesville and the Villages orthopedic surgery clinics. Participants must be 18 years or older and have a planned or scheduled primary unilateral total hip or knee arthroplasty procedure. The planned or scheduled procedure must be completed within 6 months of the last participant enrolled.

Exclusion Criteria. Patients scheduled to undergo a revision or bilateral procedure; receiving chronic opioid therapy, defined as use of opioids on most days for >3 months; or with an allergy to opioids will be excluded.

Participant Recruitment Methods. Patients typically have 2 visits to the UF Orthopedic Surgery clinic prior to surgery: an Initial Evaluation visit when the decision about surgery is made and 2) a Pre-Operative visit within 1 month of the procedure when a plan for post-operative pain management is made. During either the Initial Evaluation (decision for surgery visit) or Pre-Operative visit, patients meeting eligibility criteria will be approached by the research coordinator about study participation. The patients could also be approached via telephone, after their initial clinic evaluation to discuss consenting over the phone with the study coordinator after the physician had discussed the study during the initial evaluation appointment. The patient will be read the screening script by the coordinator to ensure the patient is eligible for the study and interested in participating. If the patient would like to enroll in the study after the screening telephone call, 2 copies of the informed consent form and a buccal cell collection kit will be mailed to the patient. Once the patient has received the research kit, the study coordinator will call the patient and read the follow up script as needed. The patient will mail the signed informed consent form and completed buccal swab sample to the study coordinator using the preaddressed paid envelope the patient will be provided. After providing written informed consent, patients will be randomly assigned to genotype-guided opioid therapy or usual pain management. A DNA sample will be collected from all patients, regardless of randomization, by saliva (via mouthwash swish and expectorate collection) or buccal cell (via buccal brush), unless venipuncture is done for other reasons and then a blood sample will be collected for genotyping. If the genotype fails with the initial sample collection, the patients will be mailed a kit for collection of a saliva or buccal cell sample for retesting.

For patients in the genotype arm, *CYP2D6* genotyping will be done in the CAP/CLIA-licensed UF Health Pathology Laboratory at Rocky Point with results reported in the EHR. It is expected that results will be reported prior to surgery in the absence of any genotyping error. Patients will be categorized as *CYP2D6* PM, IM, NM, or UM based on *CYP2D6* genotype/activity score and FDA guidance on drug interactions. Strong inhibitors (e.g. bupropion, fluoxetine, paroxetine) phenoconvert patients to PMs, with moderate inhibitors (e.g. duloxetine, fluvoxamine) reducing *CYP2D6* activity scores by 50%. Using a standardized consult note, as we are using for an on-going study in cancer pain patients (NCT02664350), recommendations will be made to avoid tramadol, hydrocodone, codeine, and oxycodone in PMs, IMs, and UMs and to use an alternative opioid (e.g. morphine, hydromorphone) or non-opioid (e.g. NSAID). Consideration of tramadol as the first line opioid will be recommended for NMs. Patients randomized to usual care will have their DNA sample collected at the Initial Evaluation visit and stored until they have completed the 2 week follow-up, at which time, the sample will be genotyped with the result reported in the EHR. This approach was successfully used in our previous study in chronic pain. Genotyping will be funded by the grant. Patients will be compensated in the amount of \$25 gift certificate for their participation. Study participation will be terminated for any patient

randomized into the usual care arm who gets genotyping done for clinical care before study completion. These patients will receive \$10 compensation for study participation.

Patients in both arms will be asked to complete surveys for PROs at the Pre-Operative visit (within 1 month of surgery) or via phone call within 30 days prior to surgery. Patients will be asked the PROMIS Pain intensity survey and about opioid consumption at 48 hours  $\pm$  24 hours and again at 1 week  $\pm$  4 days post-surgery. At 2 weeks  $\pm$  4 days post-surgery, utilizing the PROMIS measures developed with the NIH Common Fund ([www.nihpromis.org](http://www.nihpromis.org)). Surveys will be completed with the study coordinator in clinic or by telephone after their clinic visit, or if patients prefer, electronically through a link sent to them to be completed prior to their surgical procedure. Outcome measures for the proposed study were selected based on guidance in the Initiative on Methods, Measurement, and Pain Assessment in Clinical Trials (IMMPACT), which recommends that pain outcome studies assess the domains of pain, physical functioning, and emotional functioning. The specific PROs we will assess are shown in **Table 1**. These measures are well adapted for use in the clinical setting, and employ a Computer Adaptive Test (CAT) approach that minimizes respondent burden by reducing the number of questions needed to arrive at a valid PRO. We have significant experience administering the PROMIS measures to assess pain intensity using an IPAD tool from our recently completed study in patients with chronic pain. We will also assess how well patients are able to do their usual activities with the HOOS or KOOS survey.

Data will be recorded directly into the REDCap server. Patients desiring survey completion on a personal electronic device will receive a link by Short Message Service (SMS) to their cell phone using TWILIO through REDCap or email. For collection of data in those not completing surveys on personal electronic devices, or not completing them within specified time windows, we will use a call center approach to data collection. The UF Center for Quality Medication Management (CCQM) provides medication therapy management in a call-center model, with vast experience scripting for consistent data collection, and speaking to patients about drug therapy and therapy-related outcomes. Pharmacy technicians in the CCQM will be given a telephone script to use for calling study participants for survey completion.

**Data collection.** In addition to data from the PROMIS measures, we will collect the following patient information from the EHR: name, medical record number, demographics (age, sex, race, ethnicity), past medical history, social history (smoking status), surgical procedure scheduled, medications (chronic, pre-operative, post-operative, and discharge medications), use of regional anesthesia or nerve block, hospital length of stay, use of opioids at 3 and 6 months (to assess persistent opioid use). In addition, opioid consumption will be assessed at the 2 week ( $\pm$  4 day) data collection point via patient interview.

**Outcomes.** The primary outcomes are feasibility of the clinical implementation (Table 2) and opioid utilization. The secondary outcomes will be pain intensity, physical functioning, emotional functioning, and mobility at 2 weeks  $\pm$  4 days post operatively.

Table 1. PROMIS Measures to be employed	
Scales	Subscales
Pain Intensity	Worst and average pain intensity in last 7 days and current pain
PROMIS 43 (7 subscales + 1 pain intensity question)	Physical functioning: 

• Pain interference

• Physical function

• Sleep disturbance

• Social role & activities functioning

 Emotional functioning: 

• Fatigue

• Anxiety

• Depression

Others	

• Prescription pain medication misuse

**Data analysis.** For the primary analysis, we will collect data on the implementation success metrics in **Table 2**. For opioid utilization measures (morphine equivalent dose (MED), schedule IV/II opioid use), we will determine the proportion of patients prescribed specific opioids and self-reported opioid use, since patients may not take any or all of the opioid prescribed. Opioid use (proportion) will be compared between arms by  $\chi^2$  analysis or Fisher's exact test. For our secondary outcome of pain intensity, we will create a composite score of current pain and worst and average pain in last 7 days from the pain intensity subscales. We will use pain intensity at 14 days post-surgery (with a  $\pm 4$  days data capture window). Comparisons between the genotype-guided and usual care groups will be by analysis of covariance (ANOVA), adjusting for baseline pain scores and other baseline differences between the two groups and accounting for MED and/or use of opioids other than tramadol, codeine, hydrocodone, or oxycodone. While beyond the scope of this pilot, we also plan to collect data on prevalence of new persistent opioid use at 6 months (in those who were opioid naive in the year prior to the study) and differences between groups in the PRO of prescription pain medication misuse.

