**Table 2. Clinical Implementation Success metrics**

- % of patients agreeing to participate
- % of patients in genotype arm with a genotype leading to a clinical recommendation for alternative therapy
- % of patients in whom a genetic-guided recommendation is accepted by the clinician
- If recommendation is not accepted, what are the prevailing reasons
- Patient reported opioid use by CYP2D6 phenotype

**Power analysis.** We acknowledge that the proposed trial will have insufficient power to examine PROs (e.g. pain intensity). However, these data will be collected to provide preliminary data on the effects of genotype-guided therapy on PROs to inform a future larger pragmatic clinical trial, and also to document that there are not obvious trends of the genotype-guided approach leading to worse pain control, which in turn could lead to worse post-surgical outcomes. Moreover, if we assume that 25% of patients in the implementation arm will be a PM, IM, or UM (based on genotype and drug interactions) and that codeine, tramadol, hydrocodone, and oxycodone will be avoided in these patients, whereas the remaining 75% of patients in the implementation arm will be prescribed tramadol and nearly all (i.e. 95%) of controls will be prescribed tramadol, codeine, hydrocodone, or oxycodone we will have  $>80\%$  power, with an alpha of 0.05, to detect a difference in use of codeine, tramadol, hydrocodone, or oxycodone between arms.

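### Usual-care patients genotyped for clinical care are terminated after randomisation, with no continued follow-up or as-randomised analysis: a small, avoidable risk to 2-week self-reported opioid use and pain

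*Combined protocol and SAP*

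**What the plan says.** All places are in section 6 (Research Plan) of the combined protocol and SAP unless noted.

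- **Order of events.** Participant Recruitment Methods: "After providing written informed consent, patients will be randomly assigned to genotype-guided opioid therapy or usual pain management".
- **The rule.** The paragraph on genotyping ends participation for any patient "randomized into the usual care arm who gets genotyping done for clinical care before study completion" and pays that patient $10 instead of $25. No similar rule exists for the genotype-guided arm. There, a recommendation that the clinician does not accept is counted as a Table 2 metric.
- **Where the outcome data come from.** The survey paragraph: "Patients will be asked the PROMIS Pain intensity survey and about opioid consumption at 48 hours", with a second contact at 1 week and the PROMIS measures at 2 weeks. Under Data collection, "opioid consumption will be assessed at the 2 week" time point, by patient interview.
- **What these data feed.** Outcomes: "The primary outcomes are feasibility of the clinical implementation (Table 2) and opioid utilization". Pain intensity at 2 weeks is secondary. Data analysis includes "self-reported opioid use, since patients may not take any or all of the opioid prescribed" and then states: "Opioid use (proportion) will be compared between arms by" chi-square or Fisher's exact test. Table 2 also lists "Patient reported opioid use by CYP2D6 phenotype".
- **What is not said.** Outcomes, Data analysis and Power analysis name no analysis population, no as-randomised rule and no handling of terminated patients. The plan does not say whether health-record collection continues after termination, and study completion is not defined.

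**The concern.** The rule removes patients because of something that happens after randomisation, and only usual care can lose patients this way. The trigger is also close to the intervention: these are usual-care patients whose opioid choice may have been altered by a genotype result. If their prescribing looks more like that of the genotype-guided arm, leaving them out raises apparent usual-care use of the four opioids and widens the difference between arms.

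The trial is described as pragmatic, so clinical genotyping that happens to occur is part of usual care. Removing those patients changes the comparator.

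A 2-week interview that is never held cannot be recovered at analysis. Prescribing records do not fully replace it, because the plan collects self-report precisely to capture opioids that were prescribed but not taken.

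**Working it through.** **Inputs from the plan.** 320 patients (section 6), randomised 2:1 (Abstract), which gives 213 genotype-guided and 107 usual care. Planned use of the four opioids is 75% and 95%, with alpha 0.05 (Power analysis). The test is taken as two-sided because the plan does not say.

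**Assumed.** The number terminated, k = 1, 2 or 5 of 107 (0.9%, 1.9%, 4.7%), and use among the terminated of 75%, 85% or 95%. The 95% is a prescribing rate. It stands in for self-reported use, for which the plan gives no figure.

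**Step 1: the plan's own power claim.** Pooled two-proportion test:

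- Pooled proportion = (107 × 0.95 + 213 × 0.75)/320 = 0.817
- Standard error under no difference = √[0.817 × 0.183 × (1/107 + 1/213)] = 0.0458
- Standard error under the planned difference = √[0.95 × 0.05/107 + 0.75 × 0.25/213] = 0.0364
- z = (0.20 − 1.96 × 0.0458)/0.0364 = 3.03, so power is 99.9%

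The plan's figure of more than 80% is met. With a continuity correction, power is 99.8%.

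**Step 2: power after removing usual-care patients.** 99.9% with 106 or 105 left and 99.8% with 102 left. Lost power is not the problem.

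**Step 3: bias in usual-care opioid use.** Overstatement = (k/107) × (0.95 − use among the terminated), in percentage points:

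| Terminated | Use 75% | Use 85% | Use 95% |
|---|---|---|---|
| 1 | 0.19 | 0.09 | 0 |
| 2 | 0.37 | 0.19 | 0 |
| 5 | 0.93 | 0.47 | 0 |

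At 75% use, a 1-point overstatement needs 0.01 × 107/0.20 = 5.35 patients. So 6 (5.6% of the arm) are needed to exceed it, giving 1.12 points. In the extreme case where none of 5 terminated patients used the four opioids, the overstatement is 5 × 0.95/107 = 4.4 points. If health-record prescribing is kept for everyone, the shift in prescribed opioids is 0.

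**Step 4: pain at 2 weeks.** The usual-care mean shifts by k/107 for each 1-point gap between terminated and remaining patients: 0.009, 0.019 or 0.047 points, in either direction.

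**Step 5: the price of keeping them.** If the k patients stay in usual care with 75% use:

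| Kept as crossovers | Usual-care use | Difference (points) | Power |
|---|---|---|---|
| 1 | 94.8% | 19.8 | 99.8% |
| 2 | 94.6% | 19.6 | 99.8% |
| 5 | 94.1% | 19.1 | 99.6% |

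In the extreme case of 5% of the arm kept, with none using the four opioids, usual-care use is 0.95 × 95% = 90.25% and power is 92.6%, still above the plan's 80%.

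**The case against.** The case for leaving the rule alone has several parts.

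- **It will be rare.** Section 4 (Background) says genotype-guided opioid prescribing is seldom done in practice. That stands, and it is why the range is small. The same section also reports that this institution runs CYP2D6 testing for serotonin reuptake inhibitors and for opioids in primary care, so the event is possible.
- **The sizes are illustrative.** This also stands. The termination rate and the 75% are assumptions, and the 95% is a prescribing rate applied to self-report. A genotype ordered for another drug, or returned after the opioid was chosen, may change nothing.
- **The exposure is narrow.** A patient terminated after the 48-hour and 1-week contacts loses only the 2-week report. Genotyping after week 2 costs no 2-week data.
- **The missing as-randomised analysis is inferred from silence.** True: the rule ends participation and does not say that data already collected are discarded. But ending participation is explicit, and data not collected cannot be analysed under any population.
- **This is a pilot.** The plan concedes that it is underpowered for patient-reported outcomes, and four of the five Table 2 metrics are untouched. That lowers the stakes. Still, the pain data are meant to inform a larger trial and to show no obvious worsening, and one-sided loss does not help either purpose.

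These points limit the weight of the concern. None gives a reason to prefer termination over continued follow-up.

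**Conclusion.** The concern holds, at low severity. The plan contains an explicit, one-sided, post-randomisation removal that can lose part of a primary outcome (2-week self-reported opioid use) and a secondary outcome (2-week pain), and nothing elsewhere offsets it.

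With 1 to 5 of 107 terminated and their use at 75% to 95%, the overstatement of usual-care use is below 1 point against a planned 20, and it may be zero. An overstatement is the more plausible direction for opioid use but is not certain; for pain the direction is unknown. The conclusion would be less mild only with many more terminations or with terminated patients who hardly used the four opioids, and nothing in the documents points to either. Confidence is medium because the termination rate is not given.

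**What to change.** Replace the termination sentence with wording such as:

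> A usual-care patient who has CYP2D6 genotyping for clinical care stays in survey and EHR follow-up. The clinical genotype is recorded as a crossover, with date and reason. All patients are analysed in the arm to which they were randomised. Crossover counts are reported by arm, and a sensitivity analysis may exclude crossovers.

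Bring the $10 compensation sentence into line, and the consent form if it repeats the rule (the consent pages were not available for this review).

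The cost is the rewording plus up to $15 per such patient ($25 instead of $10), so $15 to $75 for 1 to 5 patients. The statistical cost is the slight dilution shown in the working.
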